8.2.2 Urine Drug Screen (UDS) and Urine Alcohol Testing

UDS will test for the following drugs of abuse: alcohol, amphetamines, barbiturates, benzodiazepines, cannabinoids, cocaine, cotinine, methadone, opiates, phencyclidine, and tricyclic antidepressants.

The results of UDS and urine alcohol testing will be listed.

8.2.3 Coagulation

A listing will be presented for coagulation data.

8.2.4 Pregnancy and Follicle Stimulating Hormone (FSH) Tests

A listing will be done for pregnancy and FSH tests. Serum pregnancy test will be done at screening. Urine pregnancy test will be done at check-in and discharge. For postmenopausal women, FSH test will be done at screening.

8.3 Vital Signs

Vital signs will include systolic and diastolic blood pressures, pulse rate, and oral body temperature.

Scheduled time points will include Days 1 and 7: Prior to morning dosing and 0.5, 1.00, 2.00, 3.00, 4.00, 6.00, 8.00, and 12.00 hours. Days 2, 4, 6, 8, 10, and 12: Prior to dosing and 4.00 and 12.00 hours postdose. Day 14: Prior to dosing and 0.5, 1.00, 2.00, 3.00, 4.00, 6.00, 8.00, 12.00, 24.00 (Day 15), 48.00 (Day 16), 72.00 (Day 17), 96.00 (Day 18) hours postdose.

At baseline on Day 1, predose vital sign measurements (except oral body temperature) will be conducted in triplicate (with an interval of approximately 10 - 30 minutes between each recording). The average value of each parameter will be considered as baseline value.

Vital signs will be summarized using descriptive statistics (n, mean, SD, minimum, median, and maximum). All vital signs, including oral temperature, will be listed. Clinically significant abnormal findings will be listed.

Summary tables on observed and change from baseline values will be presented by visit, time point, cohort and pooled placebo and overall.

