4.3.2. After First Treatment Administration

Subjects may, at any time, voluntarily withdraw from the study or be removed from the study at the discretion of an Investigator or Sponsor. If such withdrawal occurs, or if the subject fails to return for visits, an Investigator should determine the primary reason for a subject's premature withdrawal from the study and record the reason in the subject's study documents.

If a subject is withdrawn, the Sponsor will be notified and the date and reason(s) for the withdrawal will be documented in the subject's electronic Case Report Form (eCRF). If a subject

is withdrawn, the Investigator should make every effort to perform a final study visit 7 days after the last administration of the investigational product (IP) and complete the assessments and procedure outlined in the SOA. Other procedures may be performed at the Investigator's (or designee's) and/or Sponsor's discretion. If the subject is in-house, these procedures should be performed before the subject is discharged from the clinic, where possible. The Investigator (or designee) may also request that the subject return for an additional follow-up visit. All withdrawn subjects will be followed until resolution of all their AEs or until the unresolved AEs are judged by the Investigator (or designee) to have stabilized.

Subjects who are withdrawn for reasons not related to the study drug may be replaced following discussion between the Investigator and the Sponsor. Subjects withdrawn as a result of AEs thought to be related to the study drug will not be replaced.

In the case of a clinically significant illness detected during the trial (including Coronavirus Disease 2019 [COVID]-19 diagnosis), the Principal Investigator (or delegate) will, in concert with the Sponsor, determine the most appropriate course of action on an individual basis.

Evaluations will include but are not limited to:

- The safety of the subject and other study participants
- The possible effect the illness would have on the results gathered during the trial, and their ability to be appropriately analyzed or interpreted
- The possibility of suspending participation then re-initiating it after recovery
- The implication of any inclusion or exclusion criteria that would contradict possible actions
- The implication of any adherence to regulatory guidelines that may be affected by actions decided, for example group effect analysis

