4.3.2.1. Stopping Rules

4.3.2.1.1. Individual Subject Stopping Rules

A subject will be withdrawn, and study treatment discontinued, if any of the following criteria are met:

- Change in compliance with any inclusion/exclusion criterion that is clinically relevant and affects subject safety as determined by the Investigator (or designee).
Any clinically relevant sign, symptom, or intercurrent illness that, in the opinion of the Investigator (or designee), warrants subject withdrawal.

- Non-compliance with the study restrictions or other unanticipated logistical event that might affect subject safety or study assessments/objectives, or as considered applicable by the Investigator (or designee).
- Occurrence of a serious adverse event associated with active IP administration.
- A subject experiences increased ALT or AST $\geq 3 \times$ ULN.
- A subject has a creatinine $> 1.2 \times$ ULN or an increase in serum creatinine by $\geq 30 \mu\text{mol/L}$ (or 0.34 mg/dL) within 24 hours or an increase in serum creatinine to $\geq 1.5 \times$ baseline within 7 days.
- A subject has an increase of > 60 msec from baseline (predose on Day 1 of each treatment period, as applicable) in QTcF.
- A subject with any QTcF > 500 msec confirmed by the average of 2 additional ECG recordings performed at least 5 minutes apart, or other clinically significant conduction disturbance or arrhythmia.
- A subject has a heart rate < 45 bpm or heart rate > 130 bpm, confirmed by a repeat assessment
- A subject has a systolic blood pressure < 80 or > 155 mmHg, or a diastolic blood pressure > 100 mmHg, confirmed by a repeat assessment

In the event of a subject meeting any of the above withdrawal criteria, the Sponsor's Medical Monitor may deem it necessary for unblinding to occur.

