5.1 Safety Analysis Presentation

Adverse events and medical history will be classified using the Medical Dictionary for Regulatory Activities (MedDRA) terminology as defined in the study Data Management Plan (DMP).

Prior and concomitant medications will be coded with the World Health Organization Drug Dictionary (WHODrug) as defined in the study DMP.

In general, all safety summary tables will be presented for the Safety population. Summaries for AEs will be presented by treatment. Summaries for other safety endpoints will be presented by treatment if the endpoints are measured end of Study only.

In general, the data listings will include all subjects in the Randomized population up to the point of study completion or discontinuation; exceptions will be listings pertaining to a subset of subjects only (eg, subjects with protocol deviations) or a subset of records/events (eg, abnormal laboratory values). Limited data for those not included in the Randomized population, eg, who failed screening, may be presented, as appropriate.

Categorical variables will be summarized using number of observations (N), number of available data (n), and the percentage of available data (%) for each class. Continuous variables will be summarized using descriptive statistics, including N, n, arithmetic mean (mean), standard deviation (SD), minimum (min), median, and maximum (max).

The following general considerations may be applied:

- Study Day will be derived from the reference date (eg, the day of the first dose of study drug) and date of event as:
Study Day = (date of event – reference date) +1, if event is on or after the reference date;
Study Day = date of event – reference date, if event is before the reference date.
- Duration will be calculated using the general formula: (end date - start date) +1.
- If the reported value of a clinical laboratory parameter cannot be used in a statistical summary table (eg, a character string is reported for a parameter of the numerical type), a coded value may be appropriately determined and used in the statistical analyses. In general, a value below the lower limit of normal range such as ' <10 ' or ' ≤ 5 ' will be treated as half of the lower limit, '5' or '2.5', respectively, and a value above the upper limit of normal range such as ' >100 ' will be replaced with a number deemed

scientifically reasonable, eg, 101. However, the actual values as reported in the database will be presented in data listings.

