- Unscheduled assessments will not be included in descriptive summary, except for baseline consideration. When assessments are repeated for a given time point or performed at unscheduled times, only the result which is the closest to the dosing time will be included in summary tables.

In general, summary statistics for raw variables (ie, variables measured at the study site or central laboratory) will be displayed as follows:

- Minima and maxima will be displayed to the same number of decimal places as the raw data
- Means, medians, and quartiles (if presented) will be displayed to 1 additional decimal place
- Standard deviations will be displayed to 2 additional decimal places
- Percentages will be displayed to 1 decimal place; Percentages between 0 and 0.1 (exclusive) will be displayed as '<0.1'
- P-values will be displayed to 3 decimal places; P-values that are less than 0.001 will be displayed as '<0.001'

Derived variables (ie, variables that are not measured by the study site but are calculated for analysis based on other measured variables) will be displayed with the same precision as the raw data, as appropriated, then follow the similar rules in presentation of summary statistics.

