5.4 Methods for Handling Missing Data

In general, no imputations of values for missing safety data (ie, blank, “Not Done”, “Not Applicable”, etc.) will be performed and data presentations will reflect the data point as it appears in the Case Report Form (CRF) or electronic data file.

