8 SAFETY ANALYSIS

Unless otherwise specified, summary tables for safety assessments will be presented for the Safety population. All available data will be listed by cohort and subject based on the Randomized population.

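### By-visit vital-sign, ECG and laboratory summaries cover only subjects who have met no stopping rule, and the SAP plans no per-subject extreme or count of subjects crossing the limits

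*SAP*

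**What the plan says.** **Summaries.** SAP 8.3 on vital signs: "Summary tables on observed and change from baseline values will be presented by visit, time point, cohort and pooled placebo and overall". SAP 8.4 does the same by visit and time point for ventricular rate, PR, QRS and QT; QTcF is not among its parameters. SAP 8.2 summarises laboratory results by visit, with counts below, within and above the normal range, but without change from baseline.

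**Missing and extra values.** SAP 5.4 makes "no imputations of values for missing safety data". SAP 5.1 adds: "Unscheduled assessments will not be included in descriptive summary, except for baseline consideration". Where a time point has repeats, SAP 5.1 keeps one result, the one nearest to dosing.

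**Withdrawal.** Protocol 4.3.2.1.1: "A subject will be withdrawn, and study treatment discontinued, if any of the following criteria are met". The numeric criteria cover ALT/AST, creatinine, QTcF, heart rate, and systolic and diastolic pressure. For a withdrawn subject, protocol 4.3.2 asks the investigator to try to "perform a final study visit 7 days after the last administration of the investigational product". Subjects withdrawn for drug-related AEs are not replaced.

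**Listings.** SAP 5.1 says that listings generally run "up to the point of study completion or discontinuation". SAP 8 says: "All available data will be listed by cohort and subject".

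**The concern.** Absence from a later row can depend on the very measurement being summarised. Once a subject meets a limit, that subject leaves the remaining scheduled rows, and those rows describe only people who have not met a rule. Vital signs, ECG and laboratory tests are components of the primary safety endpoint, and Day 14 is the multiple-dose result.

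A crossing found only at an unscheduled reading enters no summary table, since SAP 5.1 reserves unscheduled values for baseline. SAP 8.2 to 8.4 plan neither an extreme value per subject nor a count of subjects who met each limit. Yet protocol 4.3.2.2 uses that count: two or more subjects in a cohort meeting the same individual rule, at least possibly related to treatment, bars escalation, and the MTD follows from that.

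**Working it through.** The plan has no figure to reproduce: it gives no SD, effect size or dropout rate for these endpoints.

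**1. One cohort, exact.** Protocol 3.3 gives 6 active subjects per cohort. If k are withdrawn,

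mean of all 6 − mean of those remaining = (k/6) × (mean change of withdrawn − mean change of remaining).

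For k = 1 and a gap of 10, 20 or 30 units, the later mean is off by 1.7, 3.3 or 5.0. For k = 2 it is off by 3.3, 6.7 or 10.0. QTcF illustration: one subject at +61 msec and five at +10 gives (61 + 50)/6 = 18.5 for all six, but 10.0 for the five who remain.

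**2. Chance that it arises.** The probability of at least one withdrawal among 6 is 1 − (1 − p)^6. For an assumed per-subject p of 2%, 5%, 10% or 20%, this is 11%, 27%, 47% or 74%.

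**3. Average size, systolic pressure.** From protocol 4.1 and 4.3.2.1.1: entry at 90 to 140 mmHg; withdrawal above 155, confirmed by a repeat. Assumed: baseline mean 120, SD 10; within-subject SD 5; true mean rise 10 mmHg, building from half to full effect over the first four readings; one reading on each of Days 1, 2, 4, 6, 7, 8, 10 and 12. There were 400,000 simulated subjects per row.

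| SD of rise between subjects | Withdrawn by Day 12 | Day 14 understatement (mmHg) | Cohorts of 6 with no such withdrawal | SE of a 6-subject mean change |
|---|---|---|---|---|
| 4 | 0.7% | 0.04 | 96% | 2.9 |
| 6 | 1.5% | 0.15 | 91% | 3.4 |
| 8 | 2.8% | 0.4 | 84% | 4.0 |
| 12 | 6% | 1.3 | 68% | 5.4 |
| 16 | 10% | 2.8 | 52% | 6.9 |

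The SE is √[(SD² + 25 + 25/3)/6], with a triplicate baseline. Adding the lower limit of 80 mmHg changes the last two understatements to about 1.2 and 2.6.

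A second simulation used the full vital-sign schedule, both limits, a reading SD of about 6 and a constant effect. For the same 10 mmHg rise it gave 0.2 mmHg at SD 4 and 1.0 at SD 8, with 5.5% and 9.6% withdrawn.

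**4. Direction.** This used the second set-up, with effect SD 4 to 8 and assumed baselines of diastolic 74 (SD 8) and pulse 64 (SD 9), truncated to the entry ranges.
- Diastolic +10: 21 to 26% withdrawn; rise understated by 0.7 to 2.5 mmHg.
- Pulse −10: 49% withdrawn; fall understated by 1.3 to 4.1 bpm.
- Pulse +10: 1.4 to 4.2% withdrawn; rise overstated by 0.1 to 0.5 bpm. The limit of below 45 bpm equals the lower entry bound, so it removes subjects with a low baseline and little rise.
- Pulse, no effect: 15 to 20% withdrawn; a spurious rise of 0.5 to 1.9 bpm.

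**5. Who is removed.** Only the QTcF increase rule and the creatinine-rise rules act on change. The blood-pressure, heart-rate, ALT/AST, QTcF above 500 msec and creatinine × ULN rules are absolute levels and depend heavily on baseline. When exactly one of six was removed, it was the subject with the largest change in 34 to 63% of cases in the scenarios with a systolic or diastolic rise, and in 1 to 51% of the pulse cases.

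**The case against.** The strongest reply is that little is hidden. Every row shows n, minimum and maximum, so a falling n is visible, and a crossing at a scheduled reading that is kept stays in its own row. Vital signs and laboratory data are listed in full, clinically significant findings are listed, and reasons for discontinuation and TEAEs leading to discontinuation are tabulated. No test is planned on these endpoints, and escalation rests on counts of subjects, not on Day 14 means. At 6 subjects the average bias in every row of the table is smaller than the standard error, and many cohorts would have no such withdrawal. All of this stands, and it limits the importance of the point.

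It does not close the gap. Row-wise minima and maxima do not say how many subjects ever crossed a limit, and they omit unscheduled readings. Counts above the normal range do not separate a slight elevation from 3 × ULN. A discontinuation table does not name the limit crossed. QTcF drives two stopping rules but is not summarised.

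A reader might infer that the rules remove the subjects with the largest changes, so that later means always understate the drug effect. The documents do not support this: most limits are absolute levels, and the direction can reverse. A reader might also infer that SAP 5.1 cuts off the data of withdrawn subjects. Its wording is general, discontinuation can mean leaving the study, and SAP 8 lists all available data. That is an ambiguity at most.

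**Conclusion.** The point holds in a limited form. Later by-visit summaries in SAP 8.2 to 8.4 are conditional on not having met a stopping rule, and they may be biased if a withdrawal occurs, usually toward no effect but not always.

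The size depends on assumptions that the documents do not supply. For a true systolic rise of 10 mmHg it is about 0 to 1 mmHg at an effect SD of 4 to 8, and about 1.3 to 2.8 mmHg at 12 to 16. The upper end is a high case: at SD 16, about 27% of subjects would have a fall in pressure despite the mean rise. In a single cohort, one withdrawal moves the later mean by one sixth of the gap.

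No test or sample size is affected. The addition is still worthwhile, because extremes and counts remain valid whichever way the bias runs, and the counts underlie the protocol's own escalation rule.

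**What to change.** In SAP 8.2, 8.3 and 8.4 add, for the Safety population by dose group and pooled placebo:

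1. Each subject's maximum and minimum post-baseline value and change from baseline, including repeat, unscheduled and early-termination values. Add QTcF to the ECG parameters.
2. The number of subjects ever meeting each numeric limit of protocol 4.3.2.1.1.

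Keep the by-visit tables, with a footnote explaining why n falls. Imputation is not needed.

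Minor: reconcile the listing statements in SAP 5.1 and SAP 8 so that the final-visit data of withdrawn subjects are listed and flagged. State which visit row early-termination values enter. Protocol 3.3 places those procedures at early termination and 4.3.2 places the final visit 7 days after the last dose, so these two passages also need reconciling.

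**Cost:** one extra table per domain from data already collected, with no new procedure. Extremes rise with the number of readings, so they must be read against pooled placebo on the same schedule.

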8.4 Electrocardiograms

The 12-lead ECG data will include ventricular rate, PR, QRS, QT, and interpretation.

Scheduled time points will include Days 1, 7, and 14: Predose and at 4.00, 6.00, 8.00, and 12.00 hours postdose. Days 2, 4, 6, 8, 10, and 12: Predose and 4.00 and 12.00 hours postdose. Day 14:

Prior to dosing and 0.5, 1.00, 2.00, 3.00, 4.00, 6.00, 8.00, 12.00, 24.00 (Day 15), 48.00 (Day 16), 72.00 (Day 17), 96.00 (Day 18) postdose.

At baseline in Day 1 predose, ECG recordings will be conducted in triplicate at (-45, -30, and -15 minutes). The average value of each parameter will be considered as baseline value.

12-Lead ECG data absolute and change from baseline values in ventricular rate, PR, QRS, and QT intervals) will be summarized by parameter, visit, time point using descriptive statistics (n, mean, SD, minimum, median, and maximum). Clinically significant findings in ECG data will be listed.

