4.1. Inclusion Criteria

1. Provision of signed and dated informed consent form (ICF)
2. Stated willingness to comply with all study procedures and availability for the duration of the study
3. Healthy adult male or female
4. If male, meets one of the following criteria:
 - a. Is able to procreate and agrees to use one of the accepted contraceptive regimens and not to donate sperm from the first study drug administration to at least 90 days after the follow-up visit. An acceptable method of contraception includes one of the following:
 - Abstinence from heterosexual intercourse
 - Male condom with spermicide or male condom with a vaginal spermicide (gel, foam, or suppository)

Or

- b. Is unable to procreate; defined as surgically sterile (ie, has undergone a vasectomy at least 180 days prior to the first study drug administration)
5. If female, meets one of the following criteria:
 - a. Physiological postmenopausal status, defined as the following:
 - absence of menses for at least 12 months prior to the first study drug administration (without an alternative medical condition); and
 - Follicle stimulating hormone (FSH) levels ≥ 40 mIU/mL at Screening;
6. Aged at least 18 years but not older than 59 years, inclusive, at the time of informed consent
7. Body mass index (BMI) within 18.5 kg/m^2 to 32.0 kg/m^2 , inclusively
8. Minimum body weight of at least 50.0 kg

9. Non- or ex-smoker (*An ex-smoker is defined as someone who completely stopped using nicotine products for at least 90 days prior to the first study drug administration*)
10. Must be willing to abstain from drinking coffee or caffeine containing beverages during the study, except where part of the study procedures
11. Has supine blood pressure and pulse rate within the following ranges after 5 minutes rest: systolic blood pressure 90 to 140 mmHg, diastolic blood pressure 50 to 90 mmHg, and pulse rate 45 to 90 bpm at Screening and at check in
12. Have no clinically significant diseases captured in the medical history or evidence of clinically significant findings on the physical examination (including vital signs) and/or ECG, as determined by an Investigator
13. Has clinical laboratory test results within the reference ranges of the testing laboratory, with the exception of results outside the reference ranges that are deemed not clinically significant by the Investigator (or designee) at Screening and check-in

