11. History of significant hypersensitivity, intolerance, or allergy to any drug compound, food, or other substance, unless approved by the Investigator (or designee)
12. Active neoplastic disease or history of any neoplastic disease within 5 years of Screening (except for basal or squamous cell carcinoma of the skin or carcinoma in situ that has been definitely treated with standard of care)
13. Active infection (eg, sepsis, pneumonia, abscess) or a serious infection (eg, resulting in hospitalization or requiring parenteral antibiotic treatment) within 6 weeks prior to dosing
14. History of stomach or intestinal surgery or resection that would potentially alter absorption and/or excretion of orally administered drugs (uncomplicated appendectomy and hernia repair will be allowed)
15. Any of the following at Screening and/or prior to the first study drug administration:
 - a. QT interval corrected for heart rate using Fridericia's method (QTcF) > 450 ms confirmed by repeat measurement
 - b. QRS duration > 110 ms confirmed by confirmed by repeat measurement
 - c. PR interval > 220 ms confirmed by repeat measurement
 - d. Findings which would make QTc measurements difficult or QTc data uninterpretable
 - e. History of additional risk factors for torsades de pointe (eg, heart failure, hypokalemia, family history of long QT syndrome)
16. Maintenance therapy with any drug or significant history of drug dependency or alcohol abuse (> 3 units of alcohol per day, intake of excessive alcohol, acute or chronic)
17. Positive test result for alcohol, cotinine, and/or drugs of abuse at Screening or prior to the first drug administration
18. Positive screening results to HIV Ag/Ab combo, hepatitis B surface antigen or hepatitis C virus tests
19. Any other clinically significant abnormalities in laboratory test results at Screening that would, in the opinion of an Investigator, increase the subject's risk of participation, jeopardize complete participation in the study, or compromise interpretation of study data
20. Intake of an IP in the 28 days prior to the first study drug administration
21. Use of any prescription drugs in the 28 days prior to the first study drug administration, that in the opinion of an Investigator would put into question the status of the participant as healthy

22. Use of St. John's wort in the 28 days prior to the first study drug administration and during the study

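### SAP 8.4 summarises uncorrected QT but plans no QTcF summary, although every numerical QT limit in the protocol is set on QTcF

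*SAP*

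**What the plan says.** SAP 8.4 names the ECG data: "The 12-lead ECG data will include ventricular rate, PR, QRS, QT, and interpretation". Absolute values and changes from baseline in ventricular rate, PR, QRS and QT "will be summarized by parameter, visit, time point using descriptive statistics". The section does not say by which groups; SAP 8.3, for vital signs, names cohort, pooled placebo and overall. Baseline is the mean of the Day 1 predose triplicate. The only other ECG output in 8.4 is a listing: "Clinically significant findings in ECG data will be listed".

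Neither QTcF nor any other corrected QT appears in the supplied SAP text, including its abbreviation list. SAP 12, which records changes to the protocol's analyses, does not mention it.

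The protocol uses the corrected interval throughout:

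- Protocol 4.2, exclusion 15a, names Fridericia's method and sets the limit: "QTcF) > 450 ms confirmed by repeat measurement".
- Protocol 4.3.2.1.1, first QT withdrawal rule: "A subject has an increase of > 60 msec from baseline (predose on Day 1 of each treatment period, as applicable) in QTcF".
- Protocol 4.3.2.1.1, second QT withdrawal rule: "A subject with any QTcF > 500 msec confirmed by the average of 2 additional ECG recordings performed at least 5 minutes apart".

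No numerical limit is set on uncorrected QT. Both documents list the 12-lead ECG under the primary safety endpoint.

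**The concern.** The SAP summarises one quantity and the protocol judges QT safety by another. Raw QT lengthens as the heart slows and shortens as it speeds up. A drug-related change in rate can therefore hide a QTcF rise, or produce an apparent rise with little QTcF change behind it. Someone following SAP 8.4 as written would produce a rate-dependent QT table. No planned table would show how QTcF changed by dose or how many subjects passed a limit.

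Timing adds to this. SAP 5 treats any analysis done after database lock and unblinding as post hoc and exploratory. If QTcF is added only then, the protocol's own QT measure would carry that label in the report.

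**Working it through.** The plan gives no ECG figure to reproduce. The check is a comparison of the texts (above) and a calculation of how far raw QT and QTcF can diverge.

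**Formulas.** Fridericia, with RR in seconds: RR = 60/HR, so QTcF = QT / (60/HR)^(1/3) and QT = QTcF × (60/HR)^(1/3).

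**Inputs.** The 450, 500 and 60 ms limits come from Protocol 4.2 and 4.3.2.1.1. The rate range comes from Protocol 4.1: "pulse rate 45 to 90 bpm at Screening and at check in". Baseline QTcF and the size of the rate change are assumptions, because the documents give no ECG results.

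**1. Raw QT equivalent of a fixed QTcF over the entry pulse range**

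| QTcF | 45 bpm | 60 bpm | 90 bpm |
|---|---|---|---|
| 450 ms | 495.3 | 450.0 | 393.1 |
| 500 ms | 550.3 | 500.0 | 436.8 |

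For example, 500 × (60/45)^(1/3) = 550.3 and 500 × (60/90)^(1/3) = 436.8. The raw value matching 500 ms moves by 113.5 ms across the range, so no single raw QT marks the limit.

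**2. How a 60 ms QTcF rise appears in raw QT.** Assume QTcF 400 ms at 60 bpm (raw QT 400.0), with QTcF rising to 460 ms:

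- rate goes to 70 bpm: 460 × (60/70)^(1/3) = 437.0, a change of +37.0 ms
- rate unchanged: 460.0, a change of +60.0 ms
- rate falls to 50 bpm: 460 × (60/50)^(1/3) = 488.8, a change of +88.8 ms

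**3. Sensitivity to the assumed baseline.** Baseline QTcF of 380, 400 or 420 ms and starting rate of 55, 60 or 70 bpm, for the same 60 ms rise:

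- rate up 10 bpm: +35.0 ms (420 ms, 55 bpm) to +38.8 ms (380 ms, 70 bpm)
- rate down 10 bpm: +79.0 ms (380 ms, 70 bpm) to +95.9 ms (420 ms, 55 bpm)

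**4. The reverse direction.** From 400 ms at 60 bpm, raw QT rises by 60 ms to 460 ms:

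- at 50 bpm: 460 × (50/60)^(1/3) = 432.9, a QTcF rise of 32.9 ms, well inside the 60 ms limit
- at 70 bpm: 460 × (70/60)^(1/3) = 484.3, a QTcF rise of 84.3 ms, well beyond it

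**5. Repeat recordings.** The 500 ms rule needs two additional recordings for confirmation. For repeated or unscheduled assessments, SAP 5.1 says "only the result which is the closest to the dosing time will be included in summary tables". Confirmatory ECGs after a post-dose time point would therefore drop out of the summary tables. Adding QTcF to 8.4 without an exception would leave the confirmed count without its data.

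**The case against.** The strongest case on the other side has five parts.

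*No promised analysis is missing.* The protocol leaves safety statistics to the SAP, and its QTcF limits are entry and withdrawal rules, not declared reporting thresholds. This is fair: the point is an omission in the SAP, not a broken commitment. The SAP still summarises QT for a primary endpoint component in a form that cannot be set against the protocol's limits.

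*Other outputs cover the gap.* Ventricular rate is summarised beside QT, so a mean rate shift would be visible. SAP 8 lists all available data by cohort and subject, and with 6 active and 2 placebo subjects per cohort a reader could work out QTcF by hand if QT and rate are listed. SAP 6.1 tabulates reasons for discontinuation, and SAP 8.1 counts subjects with TEAEs leading to discontinuation. All of this reduces the harm. But separate means of rate and QT do not give each subject's QTcF change, and none of these outputs is stated to give the QTcF distribution, its change, or a count beyond a limit.

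*Table layouts sit in a separate document (SAP 13) that was not supplied.* QTcF may appear there. That section covers formats and allows slight alterations; it does not define derivations or endpoints. The claim here is about what the SAP commits to.

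*The limits apply to individuals, and the summaries are of groups.* This stands. A mean QTcF would not show whether anyone crossed a limit either, which is why the counts are needed as well. The figures above are single-recording conversions and do not estimate the bias in this trial's group means.

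*The derived value could disagree with the value used during conduct.* The entry and withdrawal rules require a QTcF while the study runs. If rate is stored as a whole number (an assumption), a 0.5 bpm rounding moves a QTcF of 500 ms by about 500 × (1/3) × (0.5/60) = 1.4 ms at 60 bpm, and by up to 1.9 ms at 45 bpm. That matters only close to a limit, but the SAP should say which value governs.

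**Conclusion.** The concern holds. SAP 8.4 commits to uncorrected QT only, while all three numerical QT limits in the protocol are on QTcF. Over 45 to 90 bpm, the raw QT that corresponds to a QTcF of 500 ms runs from 550 to 437 ms. A 60 ms QTcF rise appears as roughly +35 to +39 ms in raw QT with a 10 bpm increase, and as +79 to +96 ms with a 10 bpm decrease. The change figures rest on assumed baselines (QTcF 380 to 420 ms, 55 to 70 bpm) and an assumed 10 bpm shift; they show the size of the rate dependence, not an effect expected in this trial.

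The consequence is limited to final reporting. Dose decisions run through the Safety Review Committee under its own plan (Protocol Appendix 1), which was not supplied, so nothing is claimed about stopping or escalation. The omission should be corrected before database lock.

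**What to change.** In SAP 8.4:

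- Derive QTcF = QT / RR^(1/3) for each recording, with RR = 60/ventricular rate in seconds. If the site also records QTcF, state which value is used.
- Summarise observed QTcF and its change from the Day 1 triplicate-mean baseline by visit and time point, for each cohort, pooled placebo and overall, as SAP 8.3 does for vital signs.
- Count subjects with any post-dose QTcF above 500 ms, with that value confirmed as the protocol defines it, and with a rise above 60 ms. A count above 450 ms is optional and descriptive, since the protocol uses that value only at entry.
- State that these counts use all post-dose recordings, including confirmatory repeats, as an exception to the closest-to-dosing rule in SAP 5.1.

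The cost is one derived variable, one small count table and a few sentences of SAP text. QT and ventricular rate are already collected, so the summaries and the unconfirmed counts need no new data. The confirmed count also requires the two additional recordings to be in the database and linked to the ECG that prompted them. The documents do not describe this, so data management should check it.
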